Risks from Cannabis and Dronabinol - Symptom Exacerbation: In this study, the most prominent activity associated with risk is the administration of cannabis and dronabinol, particularly to Groups 1, 2 and 3 who have a diagnosis of SCZ and a co-occurring CUD. Multiple strategies will be used to protect patients with SCZ-CUD who are given cannabis or dronabinol (or double-blinded cannabis and placebo) from relapse of psychosis. First, patients will be under treatment for their psychosis during the study, and must be stable with a low level of symptoms in order to participate. Second, all participants who will be exposed to cannabis or dronabinol during the study will be current active cannabis users who are used to the effect of cannabis. Third, with our pilot work, we have established a safe dose of dronabinol (two 7.5 mg capsules) and of cannabis for the cigarette for these patients, which did not produce untoward effects. We will use these doses in this study. All participants given cannabis or dronabinol (or double-blinded placebo cannabis and dronabinol) will be monitored closely in the laboratory until it is determined by the MD that they are able to be safely discharged. If symptoms develop and do not remit, patients will be offered inpatient treatment, as appropriate. Moreover, for participants given cannabis, dronabinol or placebo, we will attempt to contact them both the day after T2 and one week later to assess their status. If additional check-ins or clinical interventions are needed, it will be coordinated by the study team. In our pilot study with 15 patients in a similar protocol, none had problematic symptoms and no patients required additional medication or inpatient treatment. With the use of the strategies described here, study participation is unlikely to precipitate significant symptom exacerbations, but research staff, who have substantial clinical experience with this population, will be prepared to act immediately to treat patients and maintain safety if an exacerbation does occur.

Risks from Cannabis and Dronabinol - Other: Known effects of dronabinol and cannabis are listed below. These side effects occurred when people took dronabinol regularly. They are also known to occur when people smoke cannabis. We do not know how likely it is that these

side effects will occur if the medication is taken once as it will be in this study. Participants will be monitored frequently in the lab all day on the days they take these drugs.

Common side effects: A "high" feeling (e.g. laughing easily, feeling happy, having a heightened awareness)

Occasional side effects (reported in 3-30% of people): Paranoia, confusion, nervousness, sleepiness, dizziness, stomach pain, nausea with or without vomiting, tachycardia, flushed face

Rare side effects (reported in less than 3% of people): Red eyes, diarrhea and/or incontinence, depression, nightmares, trouble speaking, visual problems, ringing ears, low blood pressure

Seizures have been reported in people taking dronabinol. Patients with a history of a seizure disorder will be excluded from this study.

Recruited patients with dual diagnosis and participants with CUD (without schizophrenia) will all be frequent cannabis users. Thus, we do not expect anything more than minimal effects from the modest dose of THC in the cannabis cigarettes or the two 7.5 mg dronabinol capsules. However, as with the potential of symptom exacerbation in the dual diagnosis patients (above), we will monitor all CUD patients until it is determined by an MD that they can be safely discharged and be prepared to act immediately to provide treatment and to maintain participant safety. Moreover, participants in Groups 1-3 and Groups 5-7 will have a baseline medical history and physical assessment to rule out medical contraindications to administration of dronabinol or cannabis. The assessment will include blood pressure, EKG, complete blood count and blood chemistry screen. All women in the study will have a pregnancy test as described in the section on assessments.

Risk Related to Confidentiality: This research involves monitoring and treatment of patients who use cannabis, an illegal substance. Participants may engage in other illegal activities. Maintaining confidentiality is an area of utmost importance for this population.

To minimize risk of divulging confidential information regarding substance use or other illegal activities as well as other study information, strict attention to confidentiality will be maintained throughout every aspect of this research with standard policies and procedures, and a Certificate of Confidentiality (provided by NIDA). All members of the research team will follow the procedures to protect confidentiality adhered to by research groups at Dartmouth per the Dartmouth Committee for the Protection of Human Subjects (CPHS). Interested participants will provide permission in the form of release of information for study personnel to contact treating clinicians to discuss appropriateness of the participant's participation in the study. Participant data will be coded to protect privacy. Each patient will be assigned a unique identification number. The list of participant names and identification

numbers will be kept in a locked file cabinet separate from the database. Access to the computerized data system is carefully protected by a secured password entry system. Participants will be made aware of the various parties who will have access to their data in the informed consent document. Access to participants' data will be restricted to project investigators and other study staff on a need to know basis. Patient information, if reported, will be reported as group data or anonymously in case reports. No patients will be individually identified.

Risks from Research Assessments: The assessments being used in this study (i.e. measures of substance use, symptoms, measures of "high", mood, "liking", reward responsiveness, cognition, urine and blood assessments) may cause some discomfort, boredom, anxiety or fatigue. It is also possible, but not likely, that the SCZ participants may experience an increase in their underlying symptoms due to the process of research assessments.

Participants will be advised that they can take a break, refuse to answer question(s), or end the study session if they become uncomfortable in any way. Research staff will involve a referral site clinician to provide consultation if a patient becomes more symptomatic during a study procedure. All participating mental health agencies have emergency services that can be accessed at any time if the participant's regular clinicians are unavailable. Additionally, psychiatrists experienced in the treatment of this population, will be present or rapidly available via pager for emergency consultation at any time.

Risks from Blood Draws:

Drawing blood may involve some discomfort; the needle-stick can be slightly painful, and can cause bruising, a feeling of faintness, and in rare instances, infection at the site of the blood draw. Proper technique will be used by trained staff to minimize the likelihood of these problems. A low dose of lidocaine delivered to the skin or subcutaneously will be offered to reduce the discomfort of placing the intravenous cannula. When used in this fashion, the risks of lidocaine include:

Common: Flushing, redness of skin, swelling of skin, warm skin

Less common: Bruising, pain, itching, nausea, vomiting

Serious allergic reactions can occur. This medication should not be used for persons with a history of allergy to lidocaine or related medications.

Risks from the fMRI procedure: The scanner produces a loud banging noise and may be uncomfortable for people who have claustrophobic-like reactions in confined spaces. The long-term risks of 2 MRI scans of the brain are unknown.

Participants will be screened for metallic implants or any magnetic devices on or in their bodies prior to inclusion in the study to help ensure safety when in the MRI scanner. Participants will be warned about the possible discomforts related to MRI scanning and will be advised regarding strategies for managing these discomforts. Participants may view the scanner and scanner room prior to participation to habituate to the environment. Rest breaks will be provided as needed. Guided relaxation exercises will be provided as needed should anxiety be elevated. Participants can terminate their participation should a strong reaction occur.

Risks from Cannabis Withdrawal: Heavy cannabis users who discontinue use during the study may experience symptoms of cannabis withdrawal, involving nervousness, sleep disturbance, and appetite changes. Withdrawal from cannabis is not medically dangerous, and does not result in known long-term negative consequences. Since patients with schizophrenia tend to be light users of cannabis, we do not expect substantial cannabis withdrawal symptoms in our dual diagnosis participants. Some CUD (without SCZ) participants, if they are heavier users, may experience some withdrawal symptoms.

Participants will be educated about cannabis withdrawal with a fact sheet that includes a brief list of coping strategies. If participants experience cannabis withdrawal, research staff will cue the participant to use coping strategies and, if needed, will link the patient with clinical support from their treatment team (for patients with SCZ-CUD) or from clinical staff at DHMC (for participants with CUD alone).

Risks to Fetuses and Nursing Infants: Cannabis is known to be harmful to fetuses. Dronabinol is a pregnancy category C medication. The risks of brain fMRI for pregnant or nursing mothers to fetuses and to nursing babies are unknown. Thus, pregnant or nursing mothers will not be included in the study.

A urine pregnancy test, paid for by the study will be given to all women at the initial assessment, and on the morning of each scan day (i.e., thus before administration of cannabis, dronabinol or placebo and before scanning). If a participant is pregnant at baseline or becomes pregnant, she will be informed immediately, referred to her psychiatrist and/or her primary care physician, and discharged from the study. She will not undergo scanning nor be given cannabis or dronabinol.

Risks Related to Genetic Testing: The risks from genetic testing are mostly related to confidentiality and others (e.g. an insurer) learning a participant's results. To protect them from this type of risk, test results will be kept private. Information about participants will be coded with a number, not their name. Only the researchers in this study will be able to know the results of testing. The results of the genetic test will not be told to participants, treatment providers or others outside of the study. The results of the test will not be included in participants' medical records.

Risks Related to the Eye Camera: The eye camera LED light emits in the infrared range of the spectrum. Because the eyes do not register infrared light, it is important when using any infrared source to ensure that exposure levels on the retina, lens, or cornea will not be large enough to cause damage (e.g., burns). The LED used in the device has a much lower radiation emission than the limits defined in the appropriate standards (U.S. ANSI IESNA 27 and international IEC 62471, which govern non-laser lamps and lamp systems and their effects on eyes and skin). Specifically, at the deployment distance of 50mm or more from the eye, the intensity will be less than 4W/sr, and thus these LEDs belong to the "exempt group," considered to be of "no photobiological hazard". At a distance of 35mm or closer, the intensity would qualify as "low risk", but we will maintain the camera at a minimum of 50 mm using a fixed deployment on the head coil to ensure safety.

15. Risk/Benefit analysis:

Describe why the risks to subjects are reasonable in relation to the anticipated benefits to participants and in relation to the importance of the knowledge that may reasonably be expected to result from the study.

Participation in this study is associated with a variety of possible risks, but none of them are severe. We will obtain careful informed consent to insure that every potential participant fully understands all of the possible risks. In addition, we will not include individuals who we believe would not be able to tolerate the study procedures.

Those groups that will receive dronabinol or smoke cannabis already have a diagnosis of a CUD with recent use. For Groups 1, 2 and 3, who have comorbid diagnoses of SCZ, the use of these substances is unlikely to precipitate symptoms or side effects that are new or unusual to the participant. That was demonstrated quite clearly in the pilot study we completed. For those persons with a CUD but not SCZ, we do not believe the use of this strength of cannabis or dose of dronabinol will be unusual for them or cause any untoward effects. In the event that this is not the case, we have established intensive monitoring procedures that will allow us to detect instances in which a participant experiences adverse effects. Overall, using these strategies, we believe the risks related to participation in this study are low.

Data collected from this study will begin to improve knowledge regarding the biologic basis of cannabis use in patients with schizophrenia. Since schizophrenia is a severe disorder, and the co-occurrence of cannabis use disorder in this population presents as a significant public health problem. Cannabis use disorder contributes to the morbidity of schizophrenia through increased relapse and hospitalizations, noncompliance with treatment, and poorer overall functioning. The literature suggests that cannabis use in patients with schizophrenia may be related to cannabis' activation of brain reward circuitry, which may be dysfunctional in patients with schizophrenia. No medication treatments are currently available for the treatment of cannabis disorders, and the one medication that appears to decrease cannabis use

in patients with schizophrenia, clozapine, has side effects with severely restrict its use. The data gathered in this study will begin to expand knowledge regarding the biologic basis of cannabis use in schizophrenia, as well as to test whether dronabinol may correct the reward circuitry deficits thought to underlie this frequent, serious comorbidity. If data from this project suggest that dronabinol does improve reward circuitry impairments, it could become a candidate for study as a possible treatment for cannabis disorders in patients with schizophrenia.

The overall risk from study participation is generally low as described above. We believe that a rigorous informed consent process, in combination with the procedures described above, are adequate to prevent potential risks and to mitigate potential negative impacts of the research.

16. Research Setting

a) Is this a multi-center study?

Yes No

If yes: Are you the lead investigator? Yes No

If you are NOT the lead investigator:

Name of lead investigator:

Institution where the lead investigator is located:

b) List all sites where research will take place and the CPHS at Dartmouth College is the reviewing IRB (e.g. DHMC Alliance Hospitals, DHMC Clinics, WRJ VAMC):

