Participants will be studied using the MID task and Paced Motor task linked to fMRI, resting state functional connectivity, and the Probabilistic Reward Task (a measure of reward responsiveness). Additional assessments will include measures of psychiatric symptoms, craving for cannabis, mood, "high", "liking", cognitive measures, extrapyramidal (EPS) side effects of antipsychotic medications, and plasma levels of THC.

Following medical center guidelines, participants will be asked about symptoms of COVID-19, exposure to someone with COVID-19 and travel, and will also be assessed for fever; visits will not occur if they have symptoms or recent exposure. Participants will be required to wear a mask covering their mouth and nose, and research staff will wear protective equipment per medical center guidelines during study visits.

After completing the informed consent process, participants will be screened for study eligibility. The Baseline Neuropsychiatric Testing Visit will occur once participants have achieved 7 days of abstinence from cannabis and other substances. Once participants have achieved 14 days of abstinence, they will be assessed with the fMRI protocol and other measures twice -- at Time 1 (T1) and Time 2 (T2), each separated by a target duration of 7 days (minimum 2 days with no set maximum time interval between scan days) with continued criteria of 14 days of abstinence before T2). At T1, the assessment will occur without any intervention. At T2, the assessment will occur after administration of a double-blinded cannabis cigarette and a placebo pill for participants in Group 1; a double-blinded placebo cigarette and a dronabinol pill for participants in Group 2; and a double-blinded placebo pill and a placebo cigarette to participants in Group 3. Participants in control Groups 4 and 8 will receive no intervention at Time 2. Participants in control Groups 5, 6 and 7 (CUD without SCZ) will be studied in the same fashion as those in Groups 1, 2 and 3, i.e., with an intervention at T2.

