Protocol: Screening assessments (including medical history and physical assessment) will confirm inclusion and exclusion criteria. If participants, who are otherwise eligible, require more time to meet certain eligibility criteria (e.g., additional time to meet one month on a stable dose of antipsychotic), they may proceed to the Abstinence Period and Baseline Neuropsychiatric Assessment Visit, however, participants must meet all applicable eligibility criteria before proceeding to the T1 scan day. Patient eligibility will be reviewed by a study physician prior to the T1 Scan Day.

Abstinence Period: All study participants will be asked to refrain from any cannabis, alcohol, other substance use (except nicotine and caffeine) for a period of 14 days after the screening assessments until the day of T1, described below. (Note: If the study proves not to be feasible with a period of 14 days of abstinence, the PI will decrease the interval to 7 days as in the previous study.) Participants who are in the groups that use marijuana will be told that it can take days or weeks for THC to no longer be detected in the body, instructed about the schedule of assessments to assess/reinforce their abstinence, and educated about cannabis withdrawal. Participants will be assessed for cannabis withdrawal at each visit.) A Timeline Followback (TLFB) interview and urine/breath tests (to confirm substance abstinence) will be obtained approximately 6 times (up to 3x per week with a minimum of once per week) during this period and approximately 3 times per week with a minimum of once per week during the period between T1 and T2 for participants with a CUD. (See details below for Groups 4 and 8 who do not have any history of a substance use disorder) Those whose tests indicate abstinence will receive a \$30 credit to encourage continued abstinence. Study participants and control participants will only progress to the Scan Days of the study if they achieve 14 days of substance abstinence and will only progress to the Baseline Neuropsychiatric Assessments if they achieve 7 days of substance abstinence.

The criteria for determining abstinence will be as follows:

- For alcohol and substances other than cannabis and synthetic cannabinoids, if the person reports being abstinent on the TLFB since last assessment and tests negative for the substance, they will be considered abstinent.
- For cannabis, the following two criteria must be met for the person to be considered abstinent:

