Participants will be instructed to continue to maintain abstinence and will be given an appointment for the next fMRI testing day, as well as for a visit at their local clinic to give a urine drug screen and breathalyzer (if appropriate). To assess for possible adverse events from the procedures, participants in all groups will be contacted the day after discharge from the laboratory.

Note: If participants need an abbreviated schedule for Scan 1 to work around schedule constraints (work, school, childcare), we will accommodate this by eliminating time gaps between the events of the day. The study team may also move the start of the day earlier or later to accommodate participant schedules.

Day of T2 (to occur approximately 7 days after T1):

Groups 1, 2 and 3 (dual diagnosis participants): Prior to receiving the study capsules and study cigarette all participants in these groups will be assessed by a study physician to determine that they are stable and can safely continue with the study visit. Participants in Group 1 will receive 2 (double-blinded) placebo capsules and a 3.6%* cannabis cigarette; participants in Group 2 will receive two 7.5 mg dronabinol capsules and a placebo cigarette; and participants in Group 3 will receive two placebo capsules and a placebo cigarette. Research assessment staff will be blind to group assignment. The pill and cigarette will be dispensed at times to facilitate peak THC levels during the scans. All other procedures outlined for the T1 testing period, above, will apply. When smoking the cannabis or placebo cigarette, participants will be instructed in the use of the "Foltin" method:¹⁵⁵ "light the cigarette" (approximately 30 seconds); "prepare to smoke" (approximately 5 seconds); "inhale" (approximately 5 seconds); "hold smoke in lungs" (approximately 10 seconds); and "exhale". They will smoke 3 puffs in this manner, or until they have consumed 2/3 of the cannabis cigarette.¹⁴ Blood draws will occur for assessment of THC at set intervals. If the participant uses nicotine products blood will also be drawn to assess the person's nicotine level.

* We will obtain our cannabis cigarettes (and placebo cigarettes) from NIDA based on their available stock. We will aim for approximately 3.6% THC cigarettes for the active THC cigarettes.

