If we experience technical difficulties with the MRI scanner we may ask the participant to return to repeat appropriate study measures and the MRI scan and we would compensate accordingly.

In order to provide flexibility to study participants who may not be able to attend an appointment on the exact date of the protocol, we will allow some flexibility for scheduling appointments, but the window between Scan Days will be at least 2 days. If a participant misses a study Scan day due to illness or other unforeseen factors, s/he will be rescheduled as soon as possible. Because this population is typically unstable and often misses appointments, we expect scheduling difficulties and missed appointments to occur frequently. Research staff will work with participants to support their attendance. The maximum allowed time between the Screening Visit and the T1 Scan is 10 weeks. If a study participant goes beyond this time frame, then he or she will need to be reconsented. Also, any assessments required to establish eligibility and medical stability for the study will need to be repeated. Tasks for which the PI

believes there is no scientifically valid reason to repeat (e.g., WRAT or Baseline Neuropsychiatric Testing) will not be repeated.

Structural and Functional MRI Protocol:

Implementation: The neuroimaging protocol will be carried out at DHMC and UVM, overseen by our lead neuropsychologist. Our laboratory includes a "smoking hood", which allows for cannabis smoking in the scanner room and venting of smoke outside the laboratory. Within the scanner, participants will undergo a resting state scan, and the MID task, Paced Motor task, Aterial Spin Labeling (ASL), and (only at T1) a structural scan.

FMRI Imaging Parameters: MRI is a well-known noninvasive procedure typically used to image neuroanatomical structures. This is accomplished via the use of a high magnetic field and high frequency radio waves passing through the brain.

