Safety Assessment - Participants in Groups 1-3 and Groups 5-7 will have a baseline medical history and physical assessment to rule out medical contraindications to administration of dronabinol or cannabis. The assessment will include blood pressure, electrocardiogram (EKG), complete blood count and blood chemistry screen. All women in the study will have a pregnancy test at screening and before the scan on each scan day. Adverse events and medications that participants are receiving outside of the course of the study will be tracked and reviewed at each visit.

Other: The Behavior Rating Inventory of Executive Functions - Adult version (BRIEF-A) will be administered to gauge subjective integrity of executive functions in everyday life over the past month (Roth, Isquith, Gioia, 2015). This 75 item questionnaire takes about 10 minutes to complete. Participants will complete the measure once at the T1 session.

11. Deception.

Will deception of participants, including withheld information, be used in this research?

Yes No

If yes, complete a-d.

a) Describe the deception being used in this study:

The nature of the monetary incentive delay task and probabilistic reward task requires subjects to respond believing the speed of their response is linked to the money they earn. However all participants will receive \$35.00 for completing each of the two fMRI monetary incentive delay tasks and a total of up to \$50 for completing the three

probabilistic reward tasks, regardless of their task performance (which is based on accuracy and speed) . The instructions participants are given for the task, however, do not indicate this, but rather only say that they can win money based on their performance.

b) Explain why deception is necessary in this research:

We decided to fix the amount of winnings on each task, and thus deceive participants, so as to not disadvantage the participants with schizophrenia who tend to respond more slowly and with less accuracy than normal controls because of their illness (or related issues such as medications). Participants will not be aware that everyone receives the same amounts because it is essential in the study of reward circuitry that they believe they are "winning" additional funds, and that their winnings are dependent upon performance. This technique is used routinely by researchers across the world in order to study brain reward circuitry. Use of the same technique allows researchers to compare results across studies.

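### The 10-week expiry of screening assessments stops at the undosed T1 scan, so the baseline EKG, laboratory, physical and eligibility review have no stated maximum age at T2 dosing

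*Combined protocol and SAP*

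**What the plan says.** **Expiry rule.** The scheduling paragraph of Section 4, just before the MRI protocol, states: "The maximum allowed time between the Screening Visit and the T1 Scan is 10 weeks". Beyond that the participant must consent again, and "any assessments required to establish eligibility and medical stability for the study will need to be repeated".

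**Eligibility review.** Section 4, Protocol: "Patient eligibility will be reviewed by a study physician prior to the T1 Scan Day".

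**T1 to T2.** Section 4, Overview, gives a 7-day target and then "minimum 2 days with no set maximum time interval between scan days". The T2 heading reads "Day of T2 (to occur approximately 7 days after T1". The scheduling paragraph adds only a floor, "the window between Scan Days will be at least 2 days", and says of a participant who misses a scan day that "s/he will be rescheduled as soon as possible".

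**Dosing.** Nothing is given at T1. Groups 1-3 and 5-7 receive capsules and a cigarette at T2 only.

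**Baseline safety work-up.** Section 10, Safety Assessment, gives Groups 1-3 and 5-7 a baseline history and physical to exclude medical contraindications to the study drugs: "The assessment will include blood pressure, electrocardiogram (EKG), complete blood count and blood chemistry screen".

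**Checks on the T2 day.** A study physician must judge, before dosing, that Groups 1-3 are stable and that continuing is safe. Groups 5-7 follow the same protocol. The T1-day procedures apply again: vital signs, urine, breath and pregnancy tests, and symptom and EPS ratings for participants with schizophrenia. Section 10 has adverse events and outside medications reviewed at every visit. Section 4, Abstinence Period, has participants with CUD tested at least weekly between the scans.

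**The concern.** The plan itself holds that eligibility and medical-stability data go stale after 10 weeks. It applies that view up to a scan at which nothing is given, and not up to the one visit at which cannabis, dronabinol or placebo is given. A participant who reaches T1 one day past the limit must consent and be assessed again before an undosed scan. A participant who reaches T1 on the last permitted day can be dosed at any later date with no repeat required by that clause.

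At stake is the currency of the EKG, blood count, chemistry, physical and formal eligibility review at dosing. Those assessments exist to exclude contraindications to the drugs. Long gaps are foreseeable, since the scheduling paragraph expects missed appointments to be frequent.

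There is a smaller analytic consequence. T1 is the baseline for the Group by Time tests in Section 7, the pilot effects came from scans one week apart, and Section 7 does not say how a widely varying interval is handled.

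**Working it through.** The plan states no figure for the age of screening data at dosing, so there is nothing to reproduce. The check is day arithmetic plus a comparison of the passages.

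**Inputs**
- Maximum Screening-to-T1 interval: 10 weeks = 10 x 7 = 70 days (Section 4, scheduling paragraph).
- T1-to-T2 interval: minimum 2 days, target 7 days, no maximum (Section 4, Overview).
- Assumption: the EKG, laboratory tests, history and physical are done at the Screening Visit. If they are done later, their ages are lower by that delay.

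**Formula**

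Maximum age at T2 dosing = 70 + (T1-to-T2 interval in days)

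| T1-T2 interval | Source | Maximum age at dosing |
|---|---|---|
| 2 days | plan's minimum | 70 + 2 = 72 days |
| 7 days | plan's target | 70 + 7 = 77 days |
| 30 days | assumed, illustration only | 70 + 30 = 100 days |
| 90 days | assumed, illustration only | 70 + 90 = 160 days |
| not capped | as written | no upper limit |

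**The rule at its boundary.** T1 on day 71 triggers re-consent and repeat assessment, although nothing is given. T1 on day 70 with T2 on target means dosing on day 77 with neither.

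**What is current at dosing and what is not**

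| Item | Age at T2 dosing |
|---|---|
| Physician's stability and safety judgement | same day |
| Vital signs; pregnancy, urine and breath tests | same day |
| Psychotic, negative and EPS ratings (schizophrenia groups) | same day |
| Adverse event and medication review | same day |
| EKG, blood count, chemistry, history, physical | up to 77 days at target; uncapped |
| Formal eligibility review | T1-T2 gap plus any time by which it preceded T1; uncapped |
| Consent under the 10-week clause | up to 77 days at target; uncapped |

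**Other limits considered.** Section 13 estimates participation at about 4-6 weeks (28-42 days). That is a description and not a limit, and the 70-day allowance to T1 already exceeds it.

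**Who can be affected.** Six groups of 25 give 6 x 25 = 150 planned participants at a dosing visit. Of these, 4 x 25 = 100 (Groups 1, 2, 5 and 6) receive active drug. These are ceilings. The documents give no distribution of the interval, so the number with a long gap cannot be derived.

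**The case against.** The strongest reply is that dosing does not rest on old data. A physician must clear each participant before the capsules and cigarette, most bedside checks are repeated that day, medications are reviewed so a new prescription would be seen, and participants with CUD are seen at least weekly between scans. A longer gap therefore brings more contact. The open interval is also a stated design choice for a population that misses visits, and the passages on it agree with one another.

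Much of this stands. A reader might infer that drug can be given with no current safety assessment at all; the T2 checks contradict that. A reader might also infer that everyone in the dosed groups is affected, but someone dosed about a week after T1 is affected little. The documents likewise do not show that gaps will be longest in Groups 1-3. The interval precedes drug administration, so drug cannot lengthen it in Groups 1 or 2 relative to randomised Group 3. At most it adds noise to that contrast. In comparisons with the non-randomised Groups 4 and 8 the interval could differ, but its direction and size are unknown.

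The reply does not cover the remainder. The T2 physician check is described as a judgement of stability and safety. It is not described as a re-check of the listed criteria or a repeat of the EKG and laboratory tests. The passages agree on dates, yet the expiry rule they contain does not reach the visit for which medical stability matters most.

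**Conclusion.** The point holds in a limited form. The plan's expiry rule and formal eligibility review run only to T1, the only dosing is at T2, and the interval between them is uncapped. The baseline history, physical, EKG, blood count, chemistry and eligibility review can be up to 77 days old at dosing on the target schedule and have no upper limit as written. Same-day and weekly checks narrow this gap without closing it. Only participants in Groups 1-3 and 5-7 with a long T1-T2 interval are affected, in unknown number.

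This rests on the work-up being done at screening and on the narrative text. Section 4 refers to an attached schedule of events that was not in the text reviewed and might show a repeat on the T2 day. Confidence is therefore moderate. This is a cheap improvement; it is not evidence that participants would be dosed without safeguards, nor that the drug contrasts are biased.

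**What to change.** Reconcile the Overview, Protocol, Day of T2 and scheduling passages of Section 4 with the Safety Assessment paragraph of Section 10, so that the plan's existing re-consent and re-assessment clause is stated to apply up to the T2 dosing visit and not only to T1. Any interval is for the sponsor to set; none is proposed here. If the schedule of events already repeats these items at T2, saying so in the text would be enough.

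In Section 7, add a report of the T1-T2 interval by group (for example median, range and number far beyond target) and a sensitivity analysis of the Group by Time results that accounts for the interval.

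The cost is a wording change and one extra analysis. Some late participants would repeat assessments the plan already specifies. How many depends on the limit chosen: if the present 70 days were simply carried to T2, participants on the 7-day target who reached T1 after day 63 (70 - 7) would be caught.
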